6 STUDY PROCEDURES.....	18
7 STATISTICAL PLAN.....	21
7.1 SAMPLE SIZE DETERMINATION	21
7.2 STATISTICAL METHODS	21
7.3 SUBJECT POPULATION(S) FOR ANALYSIS	23
8 SAFETY AND ADVERSE EVENTS	23
8.1 DEFINITIONS.....	23
8.2 RECORDING OF ADVERSE EVENTS.....	27
8.3 REPORTING OF SERIOUS ADVERSE EVENTS AND UNANTICIPATED PROBLEMS	27
8.3.1 Sponsor-Investigator reporting: notifying the Mayo IRB	27
8.3.2 Sponsor-Investigator reporting: Notifying the FDA	28
8.3.3 Sponsor-Investigator reporting: Notifying the Manufacturer	28
8.4 STOPPING RULES.....	35

8.5 MEDICAL MONITORING	35
8.5.1 Internal Data and Safety Monitoring Board	35
9 DATA HANDLING AND RECORD KEEPING.....	36
9.1 CONFIDENTIALITY	36
9.2 SOURCE DOCUMENTS	36
9.3 CASE REPORT FORMS	36
9.4 RECORDS RETENTION	38
10 STUDY MONITORING, AUDITING, AND INSPECTING	38
10.1 STUDY MONITORING PLAN	38
10.2 AUDITING AND INSPECTING	38
11 ETHICAL CONSIDERATIONS	39
12 STUDY FINANCES	39
12.1 FUNDING SOURCE	39
13 PUBLICATION PLAN	39
14 REFERENCES	40

List of Abbreviations**LIST OF ABBREVIATIONS**

AE	Adverse Event/Adverse Experience
CFR	Code of Federal Regulations
CRF	Case Report Form
DSMB	Data and Safety Monitoring Board
FDA	Food and Drug Administration
GCP	Good Clinical Practice
HIPAA	Health Insurance Portability and Accountability Act
IB	Investigator's Brochure
IND	Investigational New Drug Application
IRB	Institutional Review Board
MGRS	Monoclonal gammopathy of renal significance
	Proliferative glomerulonephritis with monoclonal immunoglobulin deposition
PGNMID	Protected Health Information
PHI	
PI	Principal Investigator
SAE	Serious Adverse Event/Serious Adverse Experience
SOP	Standard Operating Procedure

Study Summary

Title	A single-center phase 2 open-label trial evaluating the efficacy and safety of daratumumab in treatment of patients with proliferative glomerulonephritis with monoclonal immune deposits and C3 glomerulopathy associated with monoclonal gammopathy
Running Title	Daratumumab in PGNMID/C3GN
Protocol Number	16-004805
Phase	Phase 2
Methodology	Open-label, Proof of Concept
Overall Study Duration	60 months
Subject Participation Duration	12 months with optional 24 month open label extension
Single or Multi-Site	Single center
Objectives	Is daratumumab effective and safe in treating patients with proliferative glomerulonephritis with monoclonal immune deposits or those with C3 glomerulopathy associated with monoclonal gammopathy
Number of Subjects	12
Diagnosis and Main Inclusion Criteria	Patients with renal biopsy consistent with membranoproliferative glomerulonephritis with monoclonal immune deposits or C3 glomerulonephropathy in addition to positive serum studies for monoclonal gammopathy within 5 years of enrollment
Study Product, Dose, Route, Regimen	For the main study, daratumumab infusions are at a dose of 16 mg/Kg once weekly for 8 doses followed by once every 2 weeks for an additional 8 doses. Patients in open-label extension (OLE) who relapse will receive 12 additional doses of daratumumab(16 mg/kg). The first 8 doses will be administered weekly and the last 4 will be given every other week.
Duration of Administration	6 months for main trial and the OLE includes a maximum of 3 courses over 24 months
Reference therapy	No reference therapy
Statistical Methodology	The incidence of treatment emergent major infection, grade 3 or 4 anemia, leukopenia or thrombocytopenia will be summarized. A paired t-test will be performed for changes in HgB, WBC count and platelet count from Baseline (Day 0) to 6 month and 12 month timepoints

1 Introduction

This document is a protocol for a human research study. This study will be carried out in accordance with the applicable United States government regulations and Mayo Clinic research policies and procedures.

1.1 Background

Monoclonal gammopathy (MG) are well known to cause kidney damage. The most common example is light chain deposition disease that occurs commonly in the setting of multiple myeloma.¹ Over the last several years, however, there is more recognition that many kidney lesions are associated with low-grade plasma cell dyscrasia or lymphoproliferative disorders.² In fact the term monoclonal gammopathy of renal significance (MGRS) has been introduced to capture kidney lesions associated with monoclonal gammopathy (MG) in the absence of multiple myeloma.³ One of the lesions commonly encountered in patients with MGRS is proliferative glomerulonephritis with monoclonal immunoglobulin deposition (PGNMID) where damage is caused by direct deposition of the monoclonals with associated inflammation.⁴⁻⁶ Another is C3 glomerulopathy (C3 GN) in the setting of MG where the monoclonals result in activation of complement pathway and indirectly result in renal injury.⁷⁻⁹ PGNMID and C3 GN associated with MG are diagnosed based on renal biopsy. Majority of patients present with hematuria and proteinuria and many have a progressive course with loss of renal function over time. Up to 70% of patients with PGNMID may have negative serum electrophoresis with immunofixation, normal serum free light chains and no clone may be identified on bone marrow biopsy.⁶ Treatment of patients with PGNMID and C3GN associated with MG should be directed towards the pathologic clone. There is currently no standardized treatment for these patients and treatments vary based on clinical practice. We currently use combination of cyclophosphamide, bortezomib and dexamethasone in patients with IgG and IgA monoclonals, and rituximab in patients with IgM monoclonals.¹⁰ The current treatments however, have had limited success rate and are associated with significant side effects. There is a desperate need for additional therapeutic options in this population. The high expression of CD38 on plasma cells and low expression on other myeloid cells makes CD38 an appealing target for monoclonal antibody therapy such as daratumumab. Daratumumab has been efficacious in treatment of patients with refractory multiple myeloma and overall is well-tolerated.¹¹ We propose use of daratumumab as first or second line agent in patients with PGNMID and C3GN associated with MG.

1.2 Investigational Agent

Daratumumab is an IgG1-kappa human monoclonal antibody that binds to the CD38 transmembrane glycoprotein on the surface of tumor cells and induces apoptosis. This process is mediated through Fc mediated cross linking and immune-mediated cell lysis through complement dependent cytotoxicity, antibody dependent cell mediated cytotoxicity and antibody dependent cellular phagocytosis. It has an elimination half-time of 18 days and volume of distribution of 4.7L. Daratumumab is FDA approved for use in treatment of multiple myeloma, however is not approved for treatment of the condition under study, PGNMID and C3 GN associated with MG. The study was submitted by the Principal Investigator to the FDA for review and granted an IND Exemption.

1.3 Clinical Data to Date

The safety and efficacy of daratumumab in patients with refractory multiple myeloma has been shown in two open-label studies. The first was a phase 1-2 study published in NEJM which evaluated the efficacy and safety of daratumumab in 42 patients. Overall 36% of patients had complete or partial response. The second study was an open label phase 2 study published in Lancet that evaluated the efficacy and safety of daratumumab in 106 patients with refractory multiple myeloma and 29 percent of patients experienced a complete or partial remission. These were patients that had failed at least 3 previous therapies. Daratumumab was overall well tolerated. Fatigue and anemia of any grade were the most common adverse events but no drug-related adverse events led to treatment discontinuation.

1.4 Dose Rationale and Risk/Benefits

The dose of daratumumab that has proven to be effective in patients with multiple myeloma is 16 mg/kg started once weekly for 8 weeks followed by every other week for 16 weeks, and then once every 4 weeks thereafter. We will be using similar dose (16 mg/kg) and similar dosing interval for a total of 16 doses over a 24 week period. The drug is only available to be administered intravenously and we aim to use the same route of administration.

Daratumumab overall is well-tolerated. The most common side-effect is infusion-related reaction (48%). We aim to use the same pre and post treatment regimen (including corticosteroid, diphenhydramine and acetaminophen) as has been done in the previous trials. Serious adverse effects include anemia, grade 3 or 4 (19%), lymphocytopenia grade 3 or 4 (40%), neutropenia, grade 3 or 4 (20%), thrombocytopenia, Grade 3 or 4 (18%), and increased risk of infection specifically pneumonia (11%). Common adverse effects include nausea (27%), anemia all grades (45%), lymphocytopenia all grades (72%), neutropenia all grades (60%), thrombocytopenia all grades (48%), backache (23%), cough (21%), upper respiratory infection (20%), fatigue (39%), fever (21%).

The treatment options for patients with PGNMID or C3GN associated with monoclonal gammopathy are limited with variable success. If untreated, majority of patients will progress to endstage renal disease. The current therapeutic options include rituximab vs. cyclophosphamide and prednisone with or without bortezomib. Daratumumab has a similar if not better side-effect profile to the above-mentioned treatment options and therefore we believe the risks associated with daratumumab are acceptable.

2 Study Objectives

Primary Objective

To assess the safety of daratumumab in patients with PGNMID or C3GN associated with monoclonal gammopathy.

Secondary Objective

To assess the efficacy of daratumumab in inducing complete or partial remission in patients with PGNMID or C3GN associated with monoclonal gammopathy as measured by change in proteinuria and serum creatinine.

3 Study Design

3.1 General Design

This study is an open-label phase 2 trial of the safety and efficacy of daratumumab, in the treatment of PGNMID and C3GN associated with monoclonal gammopathy. Subjects will be screened at outpatient Nephrology Clinic visit appointments and interested qualified subjects will be consented and offered participation in this trial. Once consent has been obtained baseline values will be established and subjects will begin treatment and follow-up for the next 12 months. Daratumumab will be administered once weekly for 8 weeks and then once every 2 weeks for 8 additional doses. Patients will be followed for a total of 12 months (6 months after the last infusion). A final visit for evaluation and collection of lab samples will be conducted at the end of the study.

3.2 *The clinical course of the patients who have achieved complete or partial remission following daratumumab is unclear, therefore these patients who have consented to the OLE and achieved complete or partial remission, will be followed for 24 months following completion of the main trial. In the OLE, patients will be assessed every 3 to 6 months. Relapse is defined as a 30% increase in proteinuria from the lowest level the patient has achieved and will be documented with two 24 hour urine collections two weeks apart. If there is evidence of relapse, patients will receive 12 additional doses of daratumumab(16 mg/kg). The first 8 doses will be given weekly and the last 4 doses will be administered every other week. Primary Endpoints*

Incidence of major infection (defined as the development of pneumonia, severe urinary tract infection/pyelonephritis, sepsis, meningitis), grade 3 or 4 anemia, leukopenia or thrombocytopenia and changes in HgB, WBC count and platelet count from baseline to 6 month and 12 month timepoints.

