3.3 Secondary Endpoints

Proportion of patients achieving complete or partial remission where the responses are defined as below:

- a) Complete Response at 12 months
 - < 300 mg proteinuria/24 hours
 - No greater than a 15% reduction in GFR as determined by creatinine clearance
- b) Partial Response at 12 months
 - > 50% reduction in 24 hour proteinuria
 - No greater than a 30% reduction in baseline GFR as determined by creatinine clearance
- c) No Response at 12 months
 - \leq 50% reduction, unchanged or increasing proteinuria over baseline levels

- A greater than a 30% reduction in baseline GFR as determined by creatinine clearance
- d) Improvement in hematuria (Categorical: <3 rbc/hpf; 3-10 rbc/hpf; 10 to 50; 50 to 100; >100 rbc/hpf)
- e) Improvement in complement 3 level (increase of 25% from baseline)

4 Subject Selection Enrollment and Withdrawal

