2 Subjects If hepatitis B results are positive HBV testing by PCR will be performed. Subjects who are positive for Anti-HBc or Anti-HBs will undergo testing for hepatitis B DNA by PCR. Subjects with serologic findings suggestive of HBV vaccination (Anti-HBs positivity as the only serologic marker) and a known history of prior HBV vaccination do not need to be tested for HBV DNA by PCR. During and following study treatment, subjects who have history of HBV infection will be closely monitored for clinical and laboratory signs of reactivation of HBV as specified in the Test and Monitoring Schedule Table above. Local law requires positive test results be reported to local health authorities.

3 If HIV or Hepatitis C test results are positive a reflex test will be conducted to confirm. Local law requires positive test results be reported to local health authorities.

4 Serum pregnancy test for women with childbearing potential.

5 Daratumumab treatment affects pre-transfusion blood testing. Therefore, in the event that a patient may need a blood transfusion Indirect Antiglobulin Testing will be performed at screening, prior to the first daratumumab infusion, and the results given to patients to carry for the duration of the study.

6 Urine pregnancy test prior to infusion for women with childbearing potential.

7 Pre-infusion medication methylprednisolone given prior to first infusion and only as needed for subsequent infusions for infusion reactions. Pre-infusion medications acetaminophen and diphenhydramine given prior to all infusions.

8 In the OLE patients will be followed clinically every 3 to 6 months, as determined by the treating nephrologist in consultation with the PI. If there is evidence of relapse defined as a 30% increase in their proteinuria from the lowest proteinuria level that the patient had achieved, patients will be treated with 12 additional doses daratumumab at 16 mg/kg.

7 Statistical Plan

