7.2 Statistical Methods

Descriptive Statistics

Univariate descriptive statistics and frequency distributions will be calculated, as appropriate for all variables. Baseline values for demographic, clinical, and outcome variables (primary and secondary) in each response category will be tabulated. Time-to-response will be analyzed descriptively with Kaplan-Meier method.

For the primary endpoint, the number and proportion of patients with treatment-emergent major infections, grade 3 or 4 anemia, leukopenia or thrombocytopenia will be summarized. Changes in Hgb, WBC count and platelet count from baseline (Day 0) will be analyzed through a paired t-test by comparing post-baseline to baseline values. The secondary endpoint of the proportion of patients with complete or partial response will be summarized in a similar manner.

It is expected that 9 patients will enter the OLE. The rate of relapse in addition to the time to relapse from the last dose of daratumumab to initiation of retreatment will be evaluated. Paired t-test will be used to evaluate change in the proteinuria from time of relapse to the end of the study. Rate of CR and PR will be evaluated at the end of the OLE.

Handling of Missing Data

This is a study of only 12 patients and expect that majority of patients will have complete data available.

Primary Hypothesis: Daratumumab is safe and well-tolerated in patients with PGNMID and C3GN associated with monoclonal gammopathy

To test this hypothesis, the incidence of major infection will be examined, specifically the development of pneumonia, severe urinary tract infection/pyelonephritis, sepsis, meningitis will be reported. In addition, anemia, leukopenia, thrombocytopenia will be examined by evaluating changes in Hgb, WBC count and platelet count, respectively. Statistical significance will be assessed using paired t-test comparing 6 months and 1 year value compared to baseline. The

number of patients who had to discontinue drug due to side effect (drop in blood counts, infection) will also be reported.

Secondary Hypothesis: Daratumumab is effective in inducing remission (defined as improvement in proteinuria and eGFR) in patients with PGNMID and C3GN associated with monoclonal gammopathy

A paired t-test will be performed to assess change in proteinuria and renal function at 6 months and 12 months compared to baseline (screening visit).

Interim Analysis

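### The open-label extension's relapse rule has no minimum proteinuria level, so a patient whose lowest value is below about 231 mg/24 h is called relapsed and retreated while still under the 300 mg/24 h complete-response limit

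*Combined protocol and SAP*

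**What the plan says.** Section 3.2 gives the reason for the OLE: "The clinical course of the patients who have achieved complete or partial remission following daratumumab is unclear". Consenting patients in complete or partial remission are followed for a further 24 months, with assessments every 3 to 6 months.

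The relapse rule in the same section is "Relapse is defined as a 30% increase in proteinuria from the lowest level the patient has achieved". It is to be documented on two 24-hour collections two weeks apart. Footnote 8 to the Test and Monitoring Schedule (section 6) gives the same threshold, "defined as a 30% increase in their proteinuria from the lowest proteinuria level that the patient had achieved", without the two collections.

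The consequence is worded as an instruction: "If there is evidence of relapse, patients will receive 12 additional doses of daratumumab(16 mg/kg", eight weekly and four every other week. Section 5.2 and footnote 8 also require the 12 doses. The Study Summary adds a cap: "the OLE includes a maximum of 3 courses over 24 months".

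Section 3.3 defines complete response at 12 months by proteinuria, "< 300 mg proteinuria/24 hours", together with a loss of GFR of no more than 15%.

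For the OLE, section 7.2 plans the relapse rate, the time from last dose to retreatment, a paired t-test of proteinuria from relapse to end of study, and a response count: "Rate of CR and PR will be evaluated at the end of the OLE".

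**The concern.** The two definitions are on different scales. Remission is an absolute level; relapse is a ratio to the patient's own lowest value. The lower that value, the smaller the absolute rise that counts as relapse, so the deepest responders need the smallest change. Nothing in the relapse rule requires that complete response be lost.

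Two things are at stake.

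- **Description of the course after remission.** The OLE is meant to show how long remission lasts. A trigger inside the complete-response range ends untreated follow-up early and records a relapse in a patient still in remission by proteinuria.
- **Exposure.** Such a patient is due a further 12-dose course. Under section 5.4, each infusion is followed by two days of dexamethasone, and antiviral and antibacterial prophylaxis continue for 3 and 6 months after the last infusion. Section 1.4 accepts the drug's risks by reference to the likely course of untreated disease. It does not discuss retreating a patient whose proteinuria is still below 300 mg/24 h.

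**Working it through.** The plan gives no figure of its own on this point, so there is none to reproduce. The check sets the two definitions against each other.

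**Inputs**
- Relapse trigger: 1.3 × lowest value (section 3.2, footnote 8).
- Complete-response limit: below 300 mg/24 h (section 3.3).
- Confirmation: two 24-hour collections two weeks apart, read here as both showing the rise (section 3.2).
- Course: 8 weekly doses, then 4 every other week (sections 3.2 and 5.2).

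**Step 1: where the trigger falls inside complete response.** This needs 1.3 × lowest < 300, so lowest < 300/1.3 = 230.8 mg/24 h.

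**Step 2: examples, with and without a 300 mg minimum.** With the minimum, the trigger becomes the larger of 1.3 × lowest and 300 mg.

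| Lowest value (mg/24 h) | Trigger now | Rise needed now | Below 300? | Trigger with minimum |
|---|---|---|---|---|
| 50 | 65 | 15 | yes | 300 |
| 100 | 130 | 30 | yes | 300 |
| 150 | 195 | 45 | yes | 300 |
| 200 | 260 | 60 | yes | 300 |
| 230 | 299 | 69 | yes | 300 |
| 231 | 300.3 | 69.3 | no | 300.3 |
| 250 | 325 | 75 | no | 325 |

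**Step 3: does anything else prevent it?** Two collections make a chance trigger less likely, but both can lie below 300 mg. The discretion in footnote 8 covers only the interval between visits. Withdrawal of consent and holding a dose for low blood counts still apply, but neither exempts a patient still below 300 mg.

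**Step 4: direction of the effect on the OLE summaries.** Every confirmed rise that meets the stricter rule (30% and 300 mg) also meets the present one, but not the reverse. For any patient, the first relapse under the present rule is therefore no later. The relapse count can only be equal or higher, and the time to relapse equal or shorter.

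**Step 5: length of one course.** Weekly doses fall on days 1 to 50, and the other four on days 64, 78, 92 and 106. That is 12 infusions over about 15 weeks.

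**The case against.** The strongest reply is that early retreatment may be wanted. Section 1.4 says most untreated patients go on to end-stage renal disease, and a confirmed doubling from 100 to 200 mg may be a real early signal. Section 3.3 defines complete response at 12 months; it does not present 300 mg as a relapse threshold. This stands as a clinical argument, and a minimum has a real cost. In an illustrative simulation (assumed log-scale SD 0.10 to 0.30, 1 to 5 earlier values, 4 assessments), detection of a true rise from 100 to 200 mg fell from about 96–100% to 0–3%. The protocol, however, nowhere says that retreatment inside complete response is intended, and gives no reason for it.

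The reach is also small. The OLE is optional and descriptive, and only patients with a lowest value below about 231 mg are affected. There may be none. That stands too.

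A reader might infer more than the documents support:

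- **That most complete responders would be falsely retreated.** Simulating a stable patient against a running minimum, with the same assumed SDs and 4 or 8 assessments, gives a false call in 5% to 98% of cases. The documents give no within-patient variability. The result is also the same at 1500 mg as at 100 mg, so it describes noise in any rule of this kind and does not size this defect.
- **That the OLE would credit retreatment with responses never lost.** Section 7.2 says only that response rates are evaluated at the end. It plans the change from relapse separately, so with about 9 patients a relapse below 300 mg would be visible.
- **That 36 extra infusions are to be expected.** 3 × 12 = 36 is the cap.

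**Conclusion.** The point holds, within limits. As written, a patient with a lowest proteinuria below 230.8 mg/24 h is classed as relapsed, and is to receive 12 infusions, at a level still under the plan's own complete-response limit. This follows from the two definitions and needs no assumption about variability. It concerns the proteinuria part of complete response only; the GFR part may or may not still be met.

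The effect is confined to the OLE: its relapse rate, its time to relapse and exposure to retreatment. The main trial's primary and secondary endpoints are untouched. About 9 patients are expected in the OLE. The documents do not say how many will be complete responders or reach so low a value, so the number affected cannot be given. This is worth changing because the change is cheap, not because it threatens the trial's main conclusions.

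**What to change.** In section 3.2, with the same wording in footnote 8, define relapse as 24-hour proteinuria at least 30% above the patient's lowest level and at least 300 mg/24 h, both met on each of two collections two weeks apart. If retreatment below 300 mg is intended, keep the rule, say so, and give the reason.

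The cost is one clause in two places, with no added visit, collection or patient. The clinical price should be stated openly: a real rise that stays below 300 mg is followed, and retreatment waits until 300 mg is reached. The trigger is unchanged for lowest values of 231 mg or more.

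The minimum does not cure chance triggers from measurement noise. Under the assumed variability above (4 or 8 assessments), false calls with the minimum in place still run from about 0.2% to 45% at a stable 250 mg and from about 3% to 76% at 280 mg. They are unchanged for partial responders at higher levels. Those patients would need a separate remedy, chosen once within-patient variability is known.

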Post-infusion: All patients should receive dexamethasone 4 mg by mouth once daily with food for two days beginning the day after daratumumab. In addition, acyclovir 400 mg by mouth twice daily, beginning within one week of starting daratumumab, and continuing for 3 months after the last daratumumab infusion. Beginning the day after their first daratumumab infusion, patients will also start single strength Bactrim once a day (or its equivalent) to prevent opportunistic infections, including pneumocystis pneumonia. Treatment with Bactrim will continue for six months after the last daratumumab infusion.

A worksheet will be created specifically for this study, which would include a dose calculation with a double check by another pharmacist for added safety. The drug will be prepared in the following steps.

1. Prepared in the non-hazardous sterile hood.
2. Drug volume calculated based upon the 16 mg/kg dose.
3. Utilize 0.9% 1000 mL for the first dose, then 0.9% 500 mL for subsequent doses.
4. Remove drug volume from 0.9% IV bag.
5. Infusion rate instructions:

Continuous Infusion: 1st and 2nd doses: Start infusion at 50 mL/hr. Rate may be increased by 50 mL/hour every hour to a maximum rate of 200 mL/hour.

Subsequent doses: Start infusion at 100 mL/hr. Rate may be increased by 50 mL/hour every hour to a maximum rate of 200 mL/hour.

6. Light protect IV bag.

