5.6 Prior and Concomitant Therapy

The patient should be off of all immunosuppressive therapies (cyclophosphamide, MMF, cyclosporine, tacrolimus, azathioprine, ACTH) within three months of enrollment in the study. If patient has received rituximab prior to the study there should be evidence of B-cell reconstitution prior to enrollment (CD 20 count >5). The subject should be off of prednisone or glucocorticoid equivalent in the last 6 weeks prior to enrollment, unless they are being treated with low dose oral prednisone or glucocorticoid for a condition unrelated to PGNMID or C3GN (e.g., asthma, gout) at a daily dose of 10mg or less.

Patients can receive ACE-I or ARB while enrolled in the study but dose adjustment is not allowed unless down titration for safety reasons.

Rescue treatment is not permitted while receiving daratumumab. If patient is failing treatment with evidence of disease progression (> 50% increase in proteinuria and > 30% reduction in GFR based on creatinine clearance) on visit day 77, the subject will be withdrawn from the study and can then receive other immunosuppressive therapy per discretion of the treating physician.

Management of Hepatitis B Virus Reactivation

Primary antiviral prophylaxis is permitted as per local standard of care. Per protocol, HBV DNA testing by PCR is mandatory for subjects at risk for HBV reactivation see Section 6.

For subjects who are diagnosed with HBV reactivation while on treatment, study treatment should be interrupted until the infection is adequately controlled. If the benefits outweigh the risks, study treatment may be resumed with concomitant antiviral prophylaxis as per local standard of care. Consult a liver disease specialist as clinically indicated.

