7.1 Sample Size Determination

This is a proof-of-concept study and therefore a power calculation was not performed. The primary endpoint of this study is the safety of this drug in terms of incidence of rate of treatment emergent major infection, grade 3 or 4 anemia, leukopenia or thrombocytopenia in patients with PGNMID and C3 GN associated with monoclonal gammopathy and the secondary endpoint is to the efficacy of daratumumab in this patient population. A paired t-test will be utilized to test the hypotheses described below. Twelve subjects will be enrolled in the study.

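### The primary hypothesis of safety and tolerability rests on a closed set of events: no named analysis counts infusion reactions, and serious infections outside four diagnoses score zero

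*Combined protocol and SAP*

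**What the plan says.** Section 2 makes safety the primary objective, and Section 7.2 (Statistical Methods) states "Primary Hypothesis: Daratumumab is safe and well-tolerated in patients with PGNMID and C3GN associated with monoclonal gammopathy". The evidence named for it is as follows.

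- **Infection.** Section 3.2 (Primary Endpoints) counts major infection, "defined as the development of pneumonia, severe urinary tract infection/pyelonephritis, sepsis, meningitis". Section 7.2 repeats the same four diagnoses as the ones to be examined.
- **Cytopenia.** Incidence of grade 3 or 4 anemia, leukopenia or thrombocytopenia, and paired t-tests of hemoglobin, white cell and platelet changes.
- **Discontinuation.** The "number of patients who had to discontinue drug due to side effect (drop in blood counts, infection) will also be reported".

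Elsewhere the protocol raises events that are not on this list.

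- Section 1.4 describes infusion-related reaction as the most common side effect, at 48%. Section 5.4 grades these reactions and uses a reaction above Grade 1 as its mark of an infusion that was poorly tolerated. Section 8.3.3.3 lists reactions of grade 3 and above, and infections of grade 4 and above at any site, as events of special interest.
- Section 5.6 provides that "For subjects who are diagnosed with HBV reactivation while on treatment, study treatment should be interrupted"; treatment may later resume.
- Section 5.4 gives prophylaxis to all patients "to prevent opportunistic infections, including pneumocystis pneumonia".

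**The concern.** The hypothesis is general, while the evidence named for it is a subset of events. Two things follow if the plan is carried out literally.

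First, tolerability would be judged without the event that the protocol itself uses to describe a poorly tolerated infusion. Second, a patient hospitalised with a serious infection at another site, and without sepsis, would count as having no major infection. Under Section 8.4 that same infection could count toward stopping the study, because the stopping rule refers to serious infection leading to discontinuation without limiting the site.

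With 12 patients and no comparator, the descriptive safety table is the main result of the trial. An event class missing from it matters more than it would in a large study with many supporting tables.

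**Working it through.** The plan has no derived figure to reproduce. Section 7.1 says "This is a proof-of-concept study and therefore a power calculation was not performed", and no threshold for safety is stated. The check is therefore a comparison of sections, followed by simple binomial arithmetic to size the omission.

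**Step 1. Which anticipated events reach the primary analysis**

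| Event | Raised in | Infection or cytopenia component | Discontinuation count |
|---|---|---|---|
| Infusion reaction | 1.4, 5.4, 8.3.3.3 | No | Only if drug is stopped for it |
| Hepatitis B reactivation | 4.2, 5.6, 6 (footnote 2) | No | Not if treatment is only interrupted |
| Severe infection at another site, no sepsis | 8.3.3.3 | No | Only if drug is stopped for it |
| Pneumocystis pneumonia | 5.4 | Yes, as pneumonia | – |
| Any infection that becomes sepsis | 3.2 | Yes | – |

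**Step 2. Infusion reactions**

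Inputs: n = 12 (Section 7.1: "Twelve subjects will be enrolled in the study"); p = 0.48 (Section 1.4). Section 1.4 gives this rate as background, apparently from myeloma, so its use here is an assumption.

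- Expected patients = n × p = 12 × 0.48 = 5.76.
- P(at least one) = 1 − (1 − p)^n = 1 − 0.52^12 = 1 − 0.0004 = 0.9996.
- At an assumed 24%: expected 12 × 0.24 = 2.88; P(at least one) = 1 − 0.76^12 = 0.963.
- At an assumed 60%: expected 12 × 0.60 = 7.2; P(at least one) is above 0.999.

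For comparison, three events that the endpoint does count, at their Section 1.4 rates:

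- pneumonia: 12 × 0.11 = 1.32
- grade 3 or 4 anemia: 12 × 0.19 = 2.28
- grade 3 or 4 thrombocytopenia: 12 × 0.18 = 2.16

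**Step 3. Infections outside the list**

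Each patient whose only serious infection is unlisted lowers the reported incidence by 1/12 = 8.3 percentage points. For illustration, two patients with a listed infection and one with an unlisted one would be reported as 2/12 = 16.7% rather than 3/12 = 25.0%.

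The documents give no rate for hepatitis B reactivation, for other serious infections or for infusion reactions of grade 3 and above. For any one of these at an assumed 1%, 5% or 10%, P(at least one in 12) = 1 − (1 − p)^12 = 0.114, 0.460 or 0.718.

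**Step 4. Precision of an added row**

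The exact (Clopper-Pearson) 95% interval for 6 of 12 is 21.1% to 78.9%. For 0 of 12 the upper limit is 1 − 0.025^(1/12) = 26.5%. An empty row would still be weak evidence of absence, so the intervals should be shown.

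**The case against.** The strongest reply is that every prespecified endpoint is a closed list, and that this one broadly follows what Section 1.4 calls serious: cytopenias and infection, chiefly pneumonia. The 48% carries no grade and stands outside that serious list. It is not uniformly the leading toxicity either: Section 1.4 gives higher all-grade rates for some cytopenias, and Section 1.3 names fatigue and anemia as the most common adverse events. This stands, and the point does not depend on rank. It depends on the hypothesis including tolerability, and on Section 5.4 tying tolerability to infusion reactions.

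A reader might infer that the plan analyses these events nowhere. The documents do not support that. Section 8.2 requires all adverse events to be recorded, Section 8.3.1 records severity on a 1 to 5 scale, Section 8.3.3.7 requires all events in report format, Section 8.5 calls for regular review of serious events, and Section 8.5.1 sends all adverse event reports to the DSMB. Section 7.2 also promises descriptive statistics for all variables, as appropriate. That sentence could cover an adverse event table, but it names none.

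A reader might also infer that the discontinuation count excludes infusion reactions. The governing term is side effect, and the bracketed items can be read as examples, so a discontinuation for an infusion reaction may well be counted.

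The infection gap is narrower than it first looks. The only opportunistic infection named in Section 5.4 is a pneumonia, sepsis from any site counts, and Section 4.2 excludes subjects positive for hepatitis B surface antigen or viral DNA. The clear omissions are serious infections at other sites without sepsis, and reactivation in subjects with resolved hepatitis B, whom Section 4.2 allows to enrol if PCR negative.

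**Conclusion.** The point holds for the endpoint and the named analysis. As written, the primary safety assessment can be completed without reporting infusion reactions, and its infection component scores zero for a serious infection outside the four diagnoses or for a hepatitis B reactivation. A reactivation that leads only to interruption misses the discontinuation count as well.

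The size for infusion reactions is about 5.8 of 12 patients if the background 48% carries over to this population. For infections it is 8.3 percentage points per patient missed, with no documented rate from which to predict how many.

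It would go too far to say that the trial could formally pass a safety test by leaving these events out. Section 7.2 sets no threshold or decision rule, so the risk is an incomplete primary safety summary, not a false positive result. The plan should be changed, but the flaw does not undermine the data, which are already collected and graded.

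**What to change.** 1. In Sections 3.2 and 7.2, define the analysed infection category as a union: the four named diagnoses at any level of seriousness, plus any other infection meeting the Section 8.1 serious criteria, plus any hepatitis B reactivation. Show the four-diagnosis incidence as a sub-row. A union is needed because Section 3.2 counts pneumonia whether or not it is serious; restricting the category to serious infections could drop events that now count.
2. Add to the Section 7.2 primary safety table the number and proportion of all-treated patients with an infusion reaction (any grade, above Grade 1, grade 3 and above), and with discontinuation for any adverse event.
3. Give each proportion an exact 95% confidence interval.
4. Give the widened category its own label. Section 4.4.1 uses the same four infections as a withdrawal criterion, so the two sections must be reconciled in a way that keeps the analysis change from altering patient management.

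The cost is endpoint and table wording and slightly more table work, from data already on the adverse event forms. Reported event rates will be the same or higher.
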